6.5. End of Study

The end of the study will be when **all** subjects have met any of the study discontinuation criteria in Section 5.7 **or** have completed at least 24 months of study participation (starting from first dose of INCB050465).

At the end of the study, subjects who have completed at least 24 months of study participation, who remain on active study treatment, and who have no evidence of progressive disease will have the option to continue on monotherapy with INCB050465 provided within a rollover Protocol, as local law permits.

6.6. Unscheduled Visits

Unscheduled visits may be held at any time at the investigator's discretion and appropriate clinical and laboratory measurements performed based on AEs or other findings.

7. CONDUCT OF STUDY ASSESSMENTS AND PROCEDURES

7.1. Administration of Informed Consent Form

Valid informed consent must be obtained from the study subject before conducting any study-specific procedures using an ICF approved by the local IRB/IEC that contains all elements required by ICH E6, and describes the nature, scope, and possible consequences of the study in a form understandable to the study subject. Local and institutional guidelines for ICF content and administration must be followed; the original signed ICF must be retained by the investigator, and a copy of the signed ICF must be provided to the study subject. The informed consent process for each subject must be documented in writing within the subject source documentation.

7.2. Interactive Response Technology Procedure

The IWRS will be contacted to obtain a subject ID number when a subject enters screening. Upon determining that the subject is eligible for enrollment, the IWRS will be contacted to obtain the treatment assignment. Additionally, the IWRS will be contacted at each regular study visit to update the study treatment supply (see Section 5.1.1 and Table 6).

7.3. Demography and Medical History

7.3.1. Demographics and Medical History

Demographic data and a complete medical and medication history, including date of diagnosis of FL, histology, current staging, grade, sites of disease, prior surgery, radiation, and other details related to the disease under study will be collected.

7.4. Prior and Concomitant Medications and Procedures

Prior and concomitant medications and procedures will be reviewed to determine subject eligibility. All concomitant medications and measures must be recorded in the eCRF, and any medication received or procedure performed within 30 days before enrollment and up to the end of study will be recorded in the eCRF. The medication record will be maintained after signing the ICF to document concomitant medications, including any changes to the dose or regimen. Concomitant medications include any prescription, over-the-counter, or natural/herbal preparations taken or administered during the study period. Concomitant treatments and/or procedures that are required to manage a subject's medical condition during the study will also be recorded in the eCRF.

For consideration of prior lines of therapy, a treatment is considered a new line of therapy if any of the following 3 conditions are met:

- Start of a new line of treatment after discontinuation of a previous line: If a treatment regimen is discontinued for any reason and a different regimen is started, it should be considered a new line of therapy. A regimen is considered to have been discontinued if all the drugs in that given regimen have been stopped. A regimen is not considered to have been discontinued if some of the drugs of the regimen, but not all, have been discontinued.
- The unplanned addition or substitution of 1 or more drugs in an existing regimen: Unplanned addition of a new drug or switching to a different drug (or combination of drugs) due to any reason is considered a new line of therapy.
- Stem cell transplant: In subjects undergoing > 1 SCT, each SCT (autologous or allogeneic) should be considered a new line of therapy regardless of whether the conditioning regimen used is the same or different.

Note: A therapy administered before an SCT, the subsequent SCT, and planned maintenance therapy after the SCT is considered 1 line of therapy.

7.5. Safety Assessments

7.5.1. Adverse Events

Adverse events will be monitored from the time the subject signs the ICF. Subjects will be instructed to report all AEs during the study and will be assessed for the occurrence of AEs throughout the study (see Section 8.1.2 and Section 8.3.2). In order to avoid bias in eliciting AEs, subjects will be asked general, nonleading questions such as "How are you feeling?" All AEs (serious and nonserious) must be recorded on the source documents and eCRFs regardless of the assumption of a causal relationship with the study drug. The definition, reporting, and recording requirements for AEs are described in Section 8.

7.5.2. Comprehensive Physical Examinations

Clinically notable abnormalities that are considered clinically significant in the judgment of the investigator are to be reported as AEs.

Physical examinations must be performed by a medically qualified individual such as a licensed physician, physician's assistant, or an advanced registered nurse practitioner, as local law permits.

The comprehensive physical examination will include height (at screening only) and the following organ or body system assessments: skin; head, eyes, ears, nose, and throat; thyroid; lungs; cardiovascular system; abdomen (liver, spleen); extremities; lymph nodes; a brief neurological examination (eg, reflexes, strength, Romberg's test, vibration sense, and gross sensory perception); and body weight (within 1 lb or 0.5 kg).

7.5.2.1. Disease-Specific Physical Examination

A disease-specific physical examination will be a symptom-directed evaluation and will include assessment(s) of the body systems or organs, as indicated by subject disease and symptoms, AEs, or other findings as determined by the investigator or designee. A disease-specific physical examination must include a measurement of the subject's body weight (within 1 lb or 0.5 kg) and an evaluation of any AEs or symptoms that the subject has previously reported.

7.5.3. Vital Signs

Vital sign measurements include blood pressure, pulse, respiratory rate, and body temperature. Blood pressure and pulse will be taken with the subject in the recumbent, semirecumbent, or sitting position after 5 minutes of rest. Clinically notable abnormalities that are considered clinically significant in the judgment of the investigator are to be reported as AEs.

7.5.4. Electrocardiograms

All 12-lead ECGs will be performed with the subject in a recumbent or semirecumbent position after 5 minutes of rest. Baseline ECGs will be obtained during screening using a single measurement but can be performed in triplicate if the single QTc measurement is > 450 milliseconds (corrected by Fridericia; see Section 3.2). Electrocardiograms will also be obtained during the Day 1 visit (triplicate measurements) before the subject receives the first dose of study drug. Triplicate ECGs will be performed predose and 1.5 hours (± 15 minutes) after receiving study treatment at the Week 4 visit. When triplicate ECGs are being obtained, individual measurements should be performed 5 minutes (± 3 minutes) apart. All 12-lead ECGs obtained at subsequent timepoints (single measurements) will be compared with the baseline 12-lead ECGs as follows:

- For ECG morphology, all postdose ECG recordings will be compared with Day 1 predose ECGs.
- For the calculation of changes in cardiac intervals (eg, QT interval), the intervals from the screening and Day 1 predose (triplicate) ECGs will be computed and averaged and used as the baseline for comparison of all postdose intervals.

If a single measurement demonstrates a QTc interval > 500 milliseconds, 2 more ECGs should be obtained over a brief period, and the averaged QTc intervals should be used to determine whether the study treatment should be interrupted.

Twelve-lead ECGs will be acquired using an ECG analysis system with analysis and printing capabilities, as well as digital transmission capabilities to a central capture module at the ECG laboratory. The investigator and research staff will receive adequate training by a qualified person on the use and operation of the analysis system. The successful digital submission of a 12-lead ECG, meeting quality standards, to the central ECG laboratory by the site must be ensured before enrollment of the first subject. The study reference manual for procedures that must be followed for the recording and transmission of ECGs and the operator's manual with instructions for operating the digital capture module will be shipped to the site along with the device. The 12-lead ECGs will be interpreted by the investigator at the site and will be used for immediate subject management. The decision to include or exclude a subject or discontinue a subject's participation in the study based on an ECG flagged as "Abnormal, Clinically

Significant" is the responsibility of the investigator, in consultation with the sponsor's medical monitor, as appropriate. Twelve-lead ECGs that are identified by the investigator as "Abnormal, Clinically Significant" will be sent to the sponsor's medical monitor for review.

The overall ECG interpretation will be indicated by a flagging system that will help distinguish between a normal ECG, ECG abnormalities where no further investigation is required, and ECG abnormalities where study exclusion, further cardiovascular investigation, and/or prompt action may be necessary depending on the clinical context. A suitable flag will be included in the "Overall ECG Interpretation" section of the report when an ECG is considered to be technically unacceptable or uninterpretable. If several different abnormalities exist corresponding to different levels of flagging, then the label will reflect the most severe level. Flagging by the central expert cardiologist of these significant abnormalities should only be regarded as a suggestion. This service is intended to assist the investigator in his/her interpretation of the ECG and decision-making. It is not intended to replace the investigator's expert judgment and knowledge of the subject's medical condition.

7.5.5. Eastern Cooperative Oncology Group Performance Status

Eastern Cooperative Oncology Group performance status ([Oken et al 1982](#); see [Appendix C](#)) will be assessed. Performance status must be assessed by a medically qualified individual and recorded in the eCRF.

7.5.6. Laboratory Assessments

Blood draws for laboratory assessments will occur at study visits indicated (see [Table 7](#)). Specific laboratory assessments are provided (see [Table 8](#)).

All laboratory assessments, including those conducted during unscheduled visits, will be performed at a central laboratory unless otherwise specified.

Note: A local laboratory assessment (including reference ranges) will be entered into the eCRF only if there is no accompanying central laboratory assessment and the local laboratory assessment caused a change in patient management (eg, a dose interruption or reduction) or was an AE or SAE.

7.5.6.1. Chemistry and Hematology

All chemistry and hematology assessments (see [Table 7](#) and [Table 8](#)) will be performed from blood samples collected using institutional best practices.

7.5.6.2. Pregnancy Testing

A serum pregnancy test will be required for all women of childbearing potential (see [Section 3.1](#)) as shown (see [Table 7](#)). At screening, the serum pregnancy test may be performed centrally or locally. Urine pregnancy tests will be conducted as shown (see [Table 7](#)). If a urine pregnancy test is positive, the results should be confirmed with a serum pregnancy test.

If the serum pregnancy test is negative after a positive urine test, the investigator will assess the potential benefit/risk to the subject and determine whether it is in the subject's best interest to resume study treatment and continue participation in the study.

7.5.6.3. Serology

Serology assessments (see [Table 8](#)) will be performed at a central laboratory.

7.5.6.4. HIV Screening Test

Subjects enrolled outside of the United States must have an HIV immunoassay test during screening to ensure negative HIV status before Day 1. This test is optional for subjects enrolled in the United States.

7.6. Efficacy Assessments

7.6.1. Computed Tomography Scan or Magnetic Resonance Imaging

Subjects will undergo a diagnostic-quality CT or MRI to evaluate measurable disease. If CT/MRI assessment was performed as standard of care before signing of the ICF but within 28 days of Day 1, then the results from that assessment must be recorded in the eCRF if used in lieu of a study-specific assessment. Assessments will be performed on the neck, chest, abdomen, and pelvis.

The disease assessment schedule also applies to those subjects who discontinue study treatment for reasons other than disease progression until disease progression, start of new anticancer therapy, withdrawal of consent, end of the study, or death, whichever occurs first. Imaging should not be delayed for interruption of study treatment.

7.6.2. Bone Marrow Examination

Bone marrow examination is required as a baseline assessment except in the following circumstances:

- Subject had a bone marrow examination performed as per standard of care within approximately 60 days from the first dose of study treatment.
- Subject had a bone marrow examination performed after the last treatment for NHL and the results showed lymphoma involvement of the bone marrow.

[figure not shown]
Subsequently, bone marrow examination will be performed and the sample(s) sent to a local histopathology laboratory to confirm CR, or as clinically indicated. [REDACTED]

[REDACTED] If the bone marrow does not have lymphoma involvement at baseline, a repeat marrow examination is not required to confirm indication of CR on imaging. [REDACTED]
[REDACTED]

All bone marrow examinations should include a unilateral aspiration and biopsy, when feasible.

[figure not shown]
The pathology report result from the bone marrow examination will be captured in the eCRF.

[figure not shown]
Note: Bone marrow biopsies and aspirates collected at screening should be evaluated locally. These materials are not to be sent to the central laboratory or the sponsor.

[figure not shown]

7.6.4. Independent Review Committee

All imaging (CT or MRI) will be submitted to the central radiology vendor for review. Imaging data and applicable clinical data will be reviewed and response assessed using the CT-based response criteria of the Lugano Classification ([Cheson et al 2014](#); see [Appendix D](#)) by independent reviewers as described in the Imaging Charter.

7.8.5. Tumor

Subjects must have an available archival tumor biopsy sample or be willing to undergo a pretreatment tumor biopsy at baseline. Tumor tissue may be obtained on study for purposes of analyzing safety, efficacy,

7.9. Other Study Procedures

7.9.1. Distribution of Subject Reminder Cards

Subjects will be provided with a reminder card at each visit.

The subject reminder card will indicate the date/time of the next visit and will also remind the subjects of which days they should not take their morning dose before coming to the clinic (see Section 7.7). The reminder cards for the Week 4 and Week 12 visits will have an area on which to record the date and time of the last dose taken (from the previous day for the Week 4 visit and most recent dose for the Week 12 visit) and the time of the most recent meal before the visit.

8. SAFETY MONITORING AND REPORTING

8.1. Adverse Events

8.1.1. Definitions

For the purposes of this Protocol, an adverse event (AE) is defined as any untoward medical occurrence associated with the use of a drug in humans, whether or not considered drug related, that occurs after a subject provides informed consent. Abnormal laboratory values or test results occurring after informed consent constitute AEs only if they induce clinical signs or symptoms, are considered clinically meaningful, require therapy (eg, hematologic abnormality that requires transfusion), or require changes in the study drugs.

8.1.2. Reporting

Adverse events that begin or worsen after informed consent should be recorded on the Adverse Events form of the eCRF. Conditions that were already present at the time of informed consent should be recorded on the Medical History form in the eCRF. Monitoring for the occurrence of new AEs should be continued for at least 30 days after the last dose of study drugs. Adverse events (including laboratory abnormalities that constitute AEs) should be described using a diagnosis whenever possible rather than by individual underlying signs and symptoms. When a clear diagnosis cannot be identified, each sign or symptom should be reported as a separate AE.

The term "disease progression" should be recorded as an AE/SAE only if there are no other identifiable AEs/SAEs associated with the disease progression at the time of reporting. For events associated with disease progression, the relevant signs and symptoms should be reported using a diagnosis whenever possible rather than individual underlying signs and symptoms. When a clear diagnosis cannot be identified, each sign or symptom should be reported as a separate AE. If the events resulting from disease progression meet the criteria for an SAE (eg, resulted in hospitalization, a life-threatening event, or death), the specific event(s) should be reported as an SAE(s) as described in Section 8.3.2. In both cases (ie, AEs or SAEs related to disease progression), it should be indicated that each event (reported as a diagnosis or as signs and symptoms) is related to disease progression on the Adverse Events form of the eCRF.

The severity of AEs will be assessed using CTCAE v4.03 (NCI 2009) Grades 1 through 5. If an event is not classified by CTCAE, the severity of the AE will be graded according to the scale below to estimate the grade of severity:

Grade 1	Mild; asymptomatic or mild symptoms; clinical or diagnostic observations only; intervention not indicated.
Grade 2	Moderate; minimal, local, or noninvasive intervention indicated; limiting age-appropriate activities of daily living.
Grade 3	Severe or medically significant but not immediately life-threatening; hospitalization or prolongation of hospitalization indicated; disabling; limiting self-care activities of daily living.
Grade 4	Life-threatening consequences; urgent intervention indicated.
Grade 5	Death due to AE

The occurrence of AEs should be sought by nondirective questioning of the subject during the screening process after signing the ICF and at each visit during the study. Adverse events may also be detected when they are volunteered by the subject during the screening process or between visits, or through physical examination, laboratory test, or other assessments. To the extent possible, each AE should be evaluated to determine:

- The severity grade (CTCAE Grade 1 to 5).
- Whether there is at least a reasonable possibility that the AE is related to the study treatment: suspected (yes) or not suspected (no).
- The start and end dates, unless unresolved at final follow-up.
- The action taken with regard to study drug.
- The event outcome (eg, not recovered/not resolved, recovered/resolved, recovering/resolving, recovered/resolved with sequelae, fatal, unknown).
- The seriousness, as per serious adverse event (SAE) definition provided in Section 8.3.1.

Unlike routine safety assessments, SAEs are monitored continuously and have special reporting requirements (see Section 8.3.2).

All AEs should be treated appropriately. If an AE is treated with a concomitant medication or nondrug therapy, this action should be recorded on Adverse Event form and the treatment should be specified on the Prior/Concomitant Medications or Procedures and Non-Drug Therapy form in the eCRF.

Once an AE is detected, it should be followed until it has resolved or until it is judged to be permanent; assessment should be made at each visit (or more frequently if necessary) of any changes in severity, the suspected relationship to the study drug, the interventions required to treat the event, and the outcome.

When the severity of an AE changes over time for a reporting period (eg, between visits), each change in severity will be reported as a separate AE until the event resolves. For example, 2 separate AEs will be reported if a subject has Grade 1 diarrhea, meeting the definition of an AE, that lasts for 3 days before worsening to a Grade 3 severity. The Grade 1 event will be reported as an AE with a start date equal to the day the event met the Grade 1 AE definition and a stop date equal to the day that the event increased in severity from Grade 1 to Grade 3. The Grade 3 event will also be reported as an AE, with the start date equal to the day the event changed in intensity from Grade 1 to Grade 3 and a stop date equal to the day that the event either changed severity again or resolved.

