5.5.2. Procedures for Study Treatment Discontinuation

If a subject discontinues study treatment, then the following should occur:

- The reason(s) for discontinuation must be documented in the subject's medical record and in the eCRF.
- The EOT visit should be performed.
- If the EOT visit coincides with a regular study visit, then the EOT evaluations will supersede those of that scheduled visit, and the data will be entered in the EOT visit in the eCRF.
- The date of the EOT visit should be recorded in the IWRS.
- Subjects must be followed for safety for no less than 30 days after the EOT visit or until study treatment–related toxicities resolve, return to baseline, or are deemed irreversible, whichever is longest.

If a subject discontinues study treatment and actively withdraws consent for collection of all follow-up data, then no additional data will be collected. However, subjects may withdraw consent for study treatment, but continue to be assessed for disease progression and survival per the schedule of assessments.

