6.4. Follow-Up

6.4.1. Safety Follow-Up

The safety follow-up period is the interval between the EOT visit and the scheduled follow-up visit, which should occur 30 to 35 days after the EOT visit (or after the last dose of study drug if the EOT visit was not performed). Adverse events and SAEs must be reported up until at least 30 days after the last dose of study drug, the date of the follow-up visit, or until toxicities resolve, return to baseline, or are deemed irreversible, whichever is longer. Reasonable efforts should be made to have the subject return for the follow-up visit and report any AEs that may occur during this period.

If a subject is scheduled to begin a new anticancer therapy before the end of the safety follow-up period, then the safety follow-up visit should be performed before new anticancer therapy is started. Once new anticancer therapy has been initiated, the subject will move into the survival follow-up period.

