The longest duration of a TEAE of any grade is defined as the longest interval between the date of occurrence of a TEAE and the date of resolution. The longest duration of a Grade 3 or higher TEAE is defined as the longest interval between the date of occurrence of a Grade 3 or higher TEAE and the date of improvement to Grade 2 or lower. If participants have missing or partial onset/end date of a TEAE, the partial or missing dates will be handled using the rules explained in Section 4.1.4. Participants who have missing end date of a TEAE at the time of analysis will be right-censored using the following algorithm:

- If the TEAE is serious, then the participant will be censored at the earlier date of data cutoff, study discontinuation, and death.
- If the TEAE is not serious,
  - If the participant is ongoing with study treatment, then the participant will be censored at the data cutoff date, OR
  - If the participant discontinued treatment, then the participant will be censored at date of safety follow-up visit, or 35 days after the end of treatment visit (or after the last dose if the end of treatment visit was not performed), whichever is later; the censored date will be truncated by the earlier date of data cutoff, study discontinuation, and death if beyond.

Longest duration of new or worsening Grade 3 or higher colitis, diarrhea, rash, and febrile neutropenia will be summarized. In addition, longest duration of new or worsening AEs of any grade will be summarized for colitis, diarrhea, and rash.

The total number of participants whose TEAE of any grade resolved or whose Grade 3 or higher TEAE improved to Grade 2 or lower and the number of participants censored will be summarized. The Kaplan-Meier estimate of median time to resolution/improvement and its 95% CIs will be provided, with the CIs calculated using the generalization of Brookmeyer and Crowley's method (1982) with log-log transformation (Klein and Moeschberger 1997). Resolution/improvement rates at selected timepoints will also be provided with 95% CIs calculated using Greenwood's formula to estimate the standard error.

TEAEs of special interest to be summarized may be adjusted based on emerging data.

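### SAP 9.2.2 caps follow-up of unresolved non-serious TEAEs after treatment stops but not of resolved ones, so Kaplan-Meier resolution rates past the cap are too high to the extent that late resolutions are recorded

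*Protocol*

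**What the plan says.** Three protocol sections ask for follow-up of adverse events beyond the safety visit. Section 8.1.2 states: "Once an AE is detected, it should be followed until it has resolved or until it is judged to be permanent". Section 6.4.1 extends post-treatment reporting past 30 days or the follow-up visit, "or until toxicities resolve, return to baseline, or are deemed irreversible, whichever is longer". Section 5.5.2 sets a similar requirement for treatment-related toxicities.

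SAP 9.2.2 measures the longest duration of a TEAE from its onset to its actual resolution date. For Grade 3 or higher events the end point is improvement to Grade 2 or lower. Censoring is limited to open events: "Participants who have missing end date of a TEAE at the time of analysis will be right-censored using the following algorithm". The rule then splits three ways:

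- Serious TEAE: censored at the earliest of data cutoff, study discontinuation and death.
- Non-serious, on treatment: "If the participant is ongoing with study treatment, then the participant will be censored at the data cutoff date".
- Non-serious, off treatment: "the participant will be censored at date of safety follow-up visit, or 35 days after the end of treatment visit", whichever is later, with the last dose standing in if there was no end-of-treatment visit. Further, "the censored date will be truncated by the earlier date of data cutoff, study discontinuation, and death if beyond", which can only move the date earlier.

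No rule truncates a resolution date that falls after this cap. The partial end-date rule in SAP 4.1.4 is bounded by study discontinuation or death, not by the cap. The outputs are a Kaplan-Meier median and, in addition, "Resolution/improvement rates at selected timepoints will also be provided". They cover colitis, diarrhea and rash (any grade and Grade 3 or higher) and febrile neutropenia (Grade 3 or higher).

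**The concern.** Take two participants who have stopped treatment, each with non-serious colitis still open at the cap. One resolves on day 90 and counts as an event at day 90. The other is known to be unresolved on day 90 but is censored at the cap. Whether follow-up past the cap counts depends on the outcome, so the censoring is informative. Among stopped participants, the risk set beyond the cap contains only those already known to resolve. An event judged permanent has no end date and is treated the same way, although its non-resolution is known.

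SAP Amendment 1 added these duration summaries to describe class-effect toxicity; they feed Table 3.2.29 and Figure 4.5.2. An upward bias would make lasting toxicity look more reversible in the participants who came off the drug.

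**Working it through.** The documents give no figure for AE resolution, so there is none to reproduce. The direction follows from the rules; the sizes below rest on assumptions.

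**Direction.** Compare the SAP rule with censoring non-resolvers at their actual last follow-up. Events and event times are the same. After the cap, each risk set R is equal or smaller under the SAP rule, so each factor 1 − d/R is equal or smaller. The resolution rate is therefore never lower and the median never longer. Before the earliest cap, measured from onset, the two curves coincide.

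**Worked example (invented data).** Twenty stopped participants have onset at end of treatment, so the cap is day 35. Eight resolve by day 33, four resolve on days 50, 65, 80 and 100, and eight never resolve (followed to day 180). After day 33, S = 12/20 = 0.60.

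- SAP rule: four remain at risk after day 35. S = 0.60 × 3/4 = 0.45 at day 50, then × 2/3 = 0.30, × 1/2 = 0.15, and 0 at day 100. Resolved: 55% at day 60, 85% at day 90, 100% at day 120. Median 50 days.
- Actual follow-up: twelve remain at risk. S = 0.60 × 11/12 = 0.55, then 0.50, 0.45, 0.40. Resolved: 45%, 55%, 60%. Median 65 days.

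**Closed form.** Assumptions: resolvers' times are exponential with median 30 days; the end-of-treatment visit is 21 days after onset, so the cap is day 21 + 35 = 56; there are no deaths; all late end dates are recorded. Let p be the share never resolving and s the share stopped.

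- Resolvers: S_r(t) = 2^(−t/30), so S_r(56) = 0.2742 and S_r(180) = 2^(−6) = 0.0156.
- S(56) = p + (1 − p) × 0.2742.
- Ratio from day 56 to day 180 under the SAP rule = [(1 − p) × 0.0156 + (1 − s)p] / [(1 − p) × 0.2742 + (1 − s)p].
- SAP rate = 1 − S(56) × ratio. True rate = (1 − p)(1 − 0.0156).

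| p | s | S(56) | Ratio | SAP rate, day 180 | True | Excess (points) |
|---|---|---|---|---|---|---|
| 10% | 40% | 0.347 | 0.241 | 91.6% | 88.6% | 3 |
| 20% | 60% | 0.419 | 0.309 | 87.0% | 78.8% | 8 |
| 30% | 60% | 0.492 | 0.420 | 79.4% | 68.9% | 10 |
| 20% | 100% | 0.419 | 0.057 | 97.6% | 78.8% | 19 |
| 30% | 100% | 0.492 | 0.057 | 97.2% | 68.9% | 28 |

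The median solves p + (1 − p) × 2^(−t/30) = 0.5. It is about day 35, 42 and 54 for p = 10%, 20% and 30%. All fall before day 56, so none is biased.

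**Capture of late end dates.** A simulation of 6,000 stopped participants used onset uniform over 0–60 days before end of treatment, 20% never resolving and a mean of 60 days for resolvers. Rates are SAP rule versus true, with a separate draw for each row.

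| Late end dates captured | Day 90 | Day 180 |
|---|---|---|
| All | 67.6% v 62.2% | 93.2% v 76.2% |
| A quarter | 65.4% v 62.6% | 91.0% v 76.4% |
| None | 61.9% v 61.7% | 62.6% v 75.7% |

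With none captured there is no overstatement: the curve simply goes flat after the last cap. With nobody permanent and all late dates captured, the bias was about zero. With 40% permanent and all late dates captured, the median did move: 82 versus 108 days.

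**The case against.** The strongest reply is that late end dates may hardly exist. Protocol Table 6 marks AE assessment at the safety visit but not under disease or survival follow-up. Section 6.4.3 lists what survival follow-up supplies, and AE status is not on the list. Section 6.4.1 moves a participant to survival follow-up once new anticancer therapy starts. On that view the cap is a sensible last-known-status date, matching the last scheduled AE assessment. This stands as a limit on certainty: a reader might infer that late resolutions are bound to be in the database, but the documents show only that they are asked for. It does not justify treating the two outcomes differently when late dates do arrive, and in the simulation capturing a quarter of them left most of the day-180 bias.

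The larger figures also need harsh inputs. In the earlier study (Protocol 1.3), diarrhea/colitis occurred in 35% of 63 subjects, about 22, while about 4 stopped for diarrhea, colitis or CMV colitis. Expected treatment is about 52 weeks, and when treatment ends months after onset the cap falls late and a 6-month rate moves little. For Grade 3 or higher summaries, improvement to Grade 2 already counts as the event, so fewer stay open. The SAP does not name its timepoints; 6 months is chosen here for illustration. All of this stands and limits the size, not the direction.

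**Conclusion.** The asymmetry is in the text of SAP 9.2.2, and its direction is certain: where some late resolutions are recorded and some events do not resolve, resolution/improvement rates beyond the cap are biased upward. Rates before the cap are unaffected. The size cannot be derived from the documents. Under the stated assumptions it runs from about 3 points at 6 months (10% never resolve, 40% stopped) to 19–28 points (20–30% never resolve, all stopped), and there is no overstatement if no late dates are captured.

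Two stronger readings are not supported. A reader might infer that median duration is generally understated; it is affected only if it falls beyond the cap, which it does not in any closed-form scenario above. A reader might also extend the point to all AE duration results or to efficacy. Serious TEAEs and TEAEs in participants still on treatment do not carry this cap, and the primary ORR analysis is not involved. These are descriptive safety summaries, and nothing is wrong with Protocol 8.1.2 itself. The SAP rule should still be corrected, because it is biased when followed as written and the repair is cheap.

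**What to change.** Amend SAP 9.2.2 in one of two ways.

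1. **Same window for both outcomes.** For non-serious TEAEs after treatment discontinuation, treat an end date later than the cap as censored at the cap. This takes one sentence and a derivation change, with no new data. The cost is that late resolution dates are discarded and little or nothing is estimated past the cap for stopped participants; the later curve then rests on those still on treatment.
2. **Use the longer follow-up.** Censor an unresolved event at the last date it was known to be ongoing, and keep an event judged permanent or irreversible as unresolved to the end of the participant's follow-up. Truncate both at data cutoff, study discontinuation or death. The second clause is needed because AE follow-up ends once an event is judged permanent, so a last-recorded-ongoing date alone would still censor those cases too early. The cost is a last-known-status date for each open AE. Where none is collected after the safety visit, that date will often be the safety visit itself.
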